1.0 Abstract

Glioblastoma (GBM) accounts for 25% of all primary central nervous system (CNS) tumors in adults and historically has been associated with median survival times of less than a year [1]. However, the addition of temozolomide to radiotherapy has resulted in significant improvements in survival, especially for certain subsets of patients [2]. With the improvement in survival times there are growing concerns about the negative effects of treatment, especially the potential for cognitive deficits after cranial radiotherapy. Decreasing the amount of brain exposed to radiation has a significant impact on cognitive function after radiation [3-5]. Proton radiotherapy is a treatment modality which has been safely and effectively used in the treatment of GBMs with low rates of toxicity such as radiation necrosis [6, 7]. Additionally, there is some pre-clinical evidence that supports greater impact on tumor cell death with protons compared to photons [8]. Previous studies have shown that intensity modulated proton therapy (IMPT) can allow for more conformal target coverage than conventional intensity modulated photon radiation therapy (IMRT) while minimizing doses to normal tissues such as the contralateral hippocampus [9]. The decreased dose to critical normal brain tissue resulting from conformal proton radiotherapy has been suggested to translate into improved cognitive function based on radiation dose cognitive effect models [10]. Additionally, improved conformality of dose delivery by IMPT may allow for dose escalation in the treatment of GBM which has been demonstrated to improve median survival time as a result of improved central control of tumors [11]. The purpose of the current study is to prospectively assess the cognitive sequelae, quality of life, and local control outcomes of patient with glioblastoma treated with IMPT versus IMRT.

2.0 Schema

Months

Eligibility Checklist

- 1. _____ Histological diagnosis of: Glioblastoma or Gliosarcoma (WHO Grade IV) adapted RPA class III, IV, or V (Y/N)
- 2. _____ Age 18 years or older at registration (Y/N)
- 3. _____ Informed consent must be signed (Y/N)
- 4. _____ Patient has a baseline Mini Mental Status Examination score of 21 or greater (Y/N)
- 5. _____ KPS ≥70 (Y/N)
- Eligible to have treatment by IMRT or IMPT as determined by radiation oncologist (Y/N)
- 7. _____ Patient is able to obtain an MRI with and without contrast with a glomerular filtration rate (eGFR) \ge 30 mg/min/1.72m² (Y/N)
- 8. _____ Patient has adequate liver, renal, and hematologic function within 14 days of registration as defined by Aspartate Amino Transferase (AST)/Alanine Amino Transferase (ALT)/Alkaline Phosphatase < 3 times normal, creatinine \leq 1.7 mg/dl, BUN \leq 35mg/dl, absolute neutrophil count \geq 1,800 cells/mm³, Hemoglobin \geq 10 g/dl, and platelet count > 100,000 (Y/N)
- 9. _____ Patient is able to adequately read, write and speak to participate in the cognitive and quality of life assessments, allowing for mild to moderate deficits in these functions due to tumor (Y/N)
- 10. _____ Patient is planning to receive concurrent temozolamide (Y/N)
- 11. _____ Patient has no prior history of brain radiation (Y/N)

- 12. _____ Patient has not had prior surgical resection of brain for other brain tumors (Y/N)
- 13. _____ Female patients of child bearing potential are not pregnant based on serum Beta-HCG test (Y/N)
- 14. _____ Patient does not have gliomatosis (Y/N)
- 15. _____ Patient has not had Glialdel (BCNU) wafers implanted (Y/N)
- 16. _____ Patient weight is less than or equal to 136 kilograms (Y/N)

3.0 Objectives

3.1 Primary Objectives

- 3.1.1 To assess whether treatment with IMPT results in longer time to cognitive failure compared with IMRT. Cognitive failure is defined as the first cognitive failure on any of the following six cognitive outcome variables: Hopkins Verbal Learning Test Revised (HVLT-R) Total Recall, HVLT-R Delayed Recall, HVLT-R Delayed Recognition, Controlled Oral Word Association (COWA), Trail Making Test (TMT) Part A or Part B.
- 3.2 Secondary Objectives
 - 3.2.1 To determine local control in the brain post radiation treatment.
 - 3.2.2 To determine overall survival in each treatment arm.
 - 3.2.3 To assess quality of life measured at two month intervals for a total of two years post-radiotherapy for both treatment arms.
 - 3.2.4 To assess the pattern of cognitive change in memory at two month intervals for two years post-treatment as well as executive function and processing speed.
 - 3.2.5 MRI diffusion weighted images (DWI) and reconstructed apparent diffusion coefficient (ADC) maps will be analyzed to see if there is a difference between pre- and post-treatment scans. These will also be analyzed for differences between the two treatment modalities.
 - 3.2.6 To evaluate if diffusion tensor imaging (DTI) correlates to the cognitive changes and if there are differences between the two treatment modalities.
 - 3.2.7 To assess the pre-treatment factors of recursive partitioning analysis (RPA) class and mini mental status examination (MMSE) in the predictive determination of local and distant control and cognitive outcome in each treatment arm.
 - 3.2.8 To assess the correlation between location of primary lesion, total volume of intracranial disease, and cognitive outcome in each treatment arm.
 - 3.2.9 To determine the relationship between MGMT promoter methylation status and cognitive and local control outcomes.
 - 3.2.10 To document and descriptively compare post-treatment adverse side effects between the two treatment arms.
 - 3.2.11 To determine the relation between dosimetric parameters and cognitive and local control outcomes.
- 3.3 Correlative objectives
 - 3.3.1 To determine if Apo E (i.e., Apo E2, Apo E3, and Apo E4) genotyping may prove to be a predictor of radiation induced neurocognitive decline (or neuro-protection).
 - 3.3.2 To determine if inflammatory markers (i.e., IL-1, IL-6, and TNF- α) may prove to be predictors of radiation induced neurocognitive decline.
 - 3.3.3 To determine if hormone and growth factors [i.e., glucocorticoids (e.g., cortisol), gonadal steroids (e.g., estradiol, testosterone, progesterone),

growth hormone, human chorionic gonadotropin (hCG), insulin-like growth factor-1 (IGF-1), and neuronal growth factor (NGF)] may prove to be a predictor of radiation induced neurocognitive decline.

3.3.4 To validate the prognostic significance of a combined multi-molecular marker survival classifier called the Molecular Clinical Prognosticator (MCP).

4.0 Background

Gliomas represent the most common primary brain tumor in the adult population. Malignant gliomas include anaplastic astryocytoma (AA) and glioblastoma multiforme (GBM) and have an annual incidence of 3 to 4 per 100,000, with over 80% of these being GBMs [12]. The standard treatment for glioblastoma is maximal safe resection followed by involved-field radiation. A pooled analysis of six randomized trials demonstrated that there is a significant survival benefit to the addition of radiation therapy after surgical resection [13]. Historically outcomes have been quite poor with median survival of less than one year for GBM [12].

Recently, combined modality treatment including the addition of concurrent and/or adjuvant temozolomide has resulted in significant improvement in outcomes for glioblastoma patients [2, 14]. Stupp et. al. demonstrated a 2 year overall survival (OS) rate of 27.2% with concomitant and adjuvant temozolomide as compared to a 10.9% 2 year OS rate with radiation alone [2]. This response was found to be durable at 5 years of follow up. Indeed, patients with favorable prognostic categories such as MGMT promoter methylation had even better survival outcomes. With improved outcomes and longer survival an increasing number of patients are at risk for secondary adverse effects from radiation treatment, particularly cognitive decline.

Cognitive function has been increasingly recognized as a key primary outcome measurement following cranial radiotherapy. Several studies have suggested that in high grade glioma patients tumor progression was the dominant cause of cognitive decline [15-17]. However, these studies were done in the era prior to the introduction of combined modality treatment when median survival was less than one year. While tumor progression is a key factor in cognitive function, prolonged survival with combined modality treatment will also lead to an increasing number of patients who develop treatment related late toxicity.

Data in low grade glioma patients suggests that the amount of brain exposed to radiation as well as the dose of radiation has a significant impact on cognitive function [3, 4, 18]. Similarly, metastatic brain cancer patients receiving stereotactic radiation have improved cognitive outcomes compared to patients treated with whole brain radiation therapy [19]. This has led to an increased interest in using more focused radiation therapy for glioblastoma.

Currently most patients with glioblastoma are treated using either 3D conformal or intensity modulated radiation therapy (IMRT) with photon beams. These modalities allow for conformal dosing to tumor while minimizing dose to surrounding normal structures. However,

surrounding normal structures continue to receive low to moderate doses of radiation. Proton beam therapy is an alternative technology which may provide more conformal dosing with less dosing to normal structures.

Proton radiotherapy has been previously demonstrated to be safe and effective in the treatment of high grade gliomas [6, 7, 20]. Additionally, there is preclinical evidence that proton radiotherapy may have a greater impact on tumor cell death. Moertel et al. have demonstrated that human glioblastoma cells in culture experience increased G2 cell cycle arrest and decreased DNA double strand break repair when irradiated with protons versus photons [8]. This suggests a potential advantage of proton therapy in glioblastoma patients.

Previous studies have also demonstrated that IMPT can allow for more conformal dosing than IMRT. IMPT can take advantage of proton characteristics such as less lateral scatter, lack of exit dose, and steep distal dose fall-off to increase conformality. For example, Rosenschold et al. compared treatment plans using IMRT versus IMPT for high grade glioma patients. They found increased planning target volume (PTV) coverage conformality with IMPT. Additionally, IMPT plans had increased sparing of healthy tissue both for whole brain doses as well as to critical structures such as the contralateral hippocampus [9].

Decreased dosage to critical normal brain tissues has been suggested to translate into improved cognitive function. Merchant et al. compared dose characteristics for four types of common childhood brain tumors treated using conformal protons versus photons and in dosevolume modeling systems found that proton plans resulted in better cognitive outcomes. Specific advantages included decreased IQ loss, less cochlea damage, and decreased endocrine effects[10]. The study of long term benefit of proton therapy in pediatric patients will require years of follow up but the preliminary results are encouraging. Similarly Arvold et al. modeled doses for protons versus photons in the treatment of benign meningiomas. They showed that protons could decrease the risk of radiation associated secondary malignancies by half and that lower doses to critical structures supporting cognitive functions such as memory including the temporal lobe and hippocampus could be achieved with proton plans [21].

While the theoretical dosimetric advantages of proton plans are intriguing we do not have randomized data comparing cognitive outcomes in glioblastoma patients treated with these two modalities. We hypothesize that IMPT will result in improved cognitive outcomes. In this trial we propose to address this question by prospectively randomizing patients with glioblastoma to treatment with IMRT versus IMPT. Patients will be stratified by RPA class, Mini Mental Status Examination score (21-26 vs. 27-30)[17], and age (less than 65 vs. 65 and older). These factors are known to have prognostic significance. The primary endpoint will be time to first cognitive failure on any of the following six cognitive test variables: HVLT-R Total Recall, HVLT-R Delayed Recall, HVLT-R Delayed Recognition, COWA, and TMT A or B. Secondary endpoints will include local control and overall survival outcomes as well as quality of life. Addressing this question in a prospective randomized fashion can be accomplished at MDACC given the high volume of cancer patients with glioblastoma treated at our center.

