12.0 Statistical Considerations

- 12.1 Randomization procedure: A stratified block randomization procedure will be used. Randomization will be performed using CORe. The randomization strata are as defined above in section 7.0, and the block size will be 6. Patients who withdraw from the study after randomization, but prior to receiving treatment will be considered a cancel and replaced.
- 12.2 Sample size: With IMRT the cognitive function failure rate at 4 months is 45%, based off of comparative analyses of the cognitive failure rate of RTOG 0614 and compared to the cognitive impairment seen on RTOG 0525; we hope to demonstrate that IMPT can achieve a cognitive function failure rate at 4 months of only 30%. We assume the time to cognitive failure in each treatment arm follows an exponential distribution. A cognitive failure rate of 45% at 4 months then implies a median time to cognitive failure of 4.6 months, while a cognitive failure rate of 30% at 4 months implies a median time to cognitive failure to cognitive failure of 7.8 months.

We will use a 1-sided significance level of 0.20 as suggested by Rubinstein et al. [51]for phase II screening trials. We expect to enroll 2 patients per month, and we will randomize 60 evaluable patients (30 to each treatment arm). We will have 80% power to detect an improvement in cognitive failure at 4 months from 45% in the IMRT arm to 30% in the IMPT arm. We expect to observe 43 events, and the analysis will be performed once we have observed these events. We define evaluable patients as those who have received the assigned treatment *and* completed baseline and at least one follow-up neurocognitive testing. We expect we will need an over accrual of 33% to account for those patients not evaluable. Therefore the target total enrollment sample size is 90 patients to accrue a total of 60 evaluable patients. We expect to observe 43 events, and we expect the trial to take 41 months to observe these events.

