- 12.3 Primary Analysis: The analysis will be performed on the intention-to-treat principle. Considering those patients who are not evaluable as treatment failures. We will use the methods of Gooley et al. [52]to estimate the cumulative incidence of cognitive failure in each treatment arm, considering progressive disease and death before cognitive failure as competing events. We will estimate the cumulative incidence of cognitive failure at 4 months with 95% confidence intervals. We will use the methods of Fine and Gray [53]to test for a difference between treatment arms with respect to the cumulative incidence of cognitive failure, considering progressive disease and death before and death before and death before cognitive failure as competing events. We will use the methods of Fine and Gray [53]to test for a difference between treatment arms with respect to the cumulative incidence of cognitive failure, considering progressive disease and death before cognitive failure as competing events. Our model will include treatment arm and the stratification factors used at randomization.
- 12.4 Secondary Analysis:

We will repeat the primary analysis on only those patients considered evaluable. All the secondary analyses described below will be performed using all patients as well as using only evaluable patients. We will estimate the cumulative incidence of local failure using the methods of Gooley et al. considering death as a competing event. We will model the time to local failure using the methods of Fine and Gray to test for differences between treatment arms, considering death as a competing event. Our model will include treatment arm and the stratification factors used at randomization, as well as selected dosimetric parameters. We will similarly analyze time to distant failure.

We will use the product limit estimator of Kaplan and Meier [54] to estimate overall survival stratified by treatment arm. We will also use Cox proportional hazards regression [55] to model overall survival as a function of treatment arm and the stratification factors used at randomization.

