We will use descriptive statistics to summarize by treatment arm the quality of life data at each assessment time. We will also use boxplots to summarize the quality of life data by treatment arm at each assessment time. We will model the quality of life data using mixed effects regression methods with repeated measures. The model will include treatment arm, selected dosimetric parameters, baseline cognitive function, location of the primary tumor (left vs. right hemisphere, if bilateral disease is present, location will be determined by the hemisphere with highest burden of disease), and the stratification factors used at randomization as fixed effects and patient as a random effect. We will similarly analyze the cognitive tests. For nearly all the prior mentioned analyses we will also plan to conduct an as-treated analysis.

We will tabulate by treatment arm the adverse events by grade and relationship to treatment.

We will use logistic regression methods to model the logit of the probability of neurocognitive decline as function of ApoE (i.e., Apo E2, Apo E3, Apo E4) genotyping, inflammatory markers (i.e., IL-1, IL-6, TNF- α), and hormone growth factors (i.e., glucocorticoids, gonadal steroids, growth hormone, human chorionic gonadotrpin, insulin-like growth factor-1, neuronal growth factor).

Determination of MCP class will be determined by RPA analysis using results of MGMT, *IDH1*, G-CIMP, and mRNA assays as well as RTOG RPA class. We will use descriptive statistics to report class distributions overall and by treatment arm. Survival by classes will be visualized on Kaplan/Meier plots, compared by the logrank test. The Cox proportional hazards regression will be used to model MCP classification, adjusting for treatment arm and stratification factors.

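### The primary cognitive-failure model leaves out tumour hemisphere, which 12.4 adjusts for when it models the same tests, so nothing pre-specified corrects the primary estimate if the arms differ by side

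*Combined protocol and SAP*

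**What the plan says.** Sections 4.0 and 7.1 stratify randomisation by three factors: "Patients will be stratified by RPA class, Mini Mental Status Examination score (21-26 vs. 27-30)[17], and age (less than 65 vs. 65 and older". Section 7.1.1 gives the RPA split as III or IV against V. For the primary endpoint, 12.3 specifies a Fine-Gray model with progression and death as competing events, and states: "Our model will include treatment arm and the stratification factors used at randomization". No other covariate is named.

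Section 12.4 describes a mixed model for quality of life and says the cognitive tests will be handled in the same way. Its fixed effects include "location of the primary tumor (left vs. right hemisphere, if bilateral disease is present", with bilateral cases assigned to the side carrying more disease. Objective 3.2.8 is "To assess the correlation between location of primary lesion, total volume of intracranial disease, and cognitive outcome in each treatment arm". The stated variants of the primary analysis are the evaluable-patient and as-treated repeats. Neither adds a location term.

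**The concern.** The primary endpoint (10.1.1) is the first reliable decline on any of six variables from the cognitive tests. The plan adjusts its secondary analysis of those tests for tumour side, but not its primary one, and gives no reason. Side is known before treatment and is not balanced by the stratification.

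The trial is small, so the arms may well differ by side. If side affects the rate of cognitive failure, the arm comparison then carries part of that difference. The planned model would not remove it, and an adjustment added after the imbalance was seen would carry little weight. The decision rule leaves room for this to matter: "We will use a 1-sided significance level of 0.20".

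**Working it through.** **1. The plan's own figure.** Section 12.2 assumes exponential times: "A cognitive failure rate of 45% at 4 months then implies a median time to cognitive failure of 4.6 months". The IMPT target is a 30% failure rate at 4 months.

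- HR = ln(0.70)/ln(0.55) = 0.597, so ln HR = -0.516.
- Schoenfeld events, one-sided 0.20, 80% power: 4 × (0.842 + 0.842)² / 0.516² = 42.5, rounded up to 43.
- Power with 43 events: 80.3%.

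The stated 43 events and 80% power reproduce.

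**2. How often the arms differ by side.** The documents do not give the share of left-sided tumours; 50% is assumed. The between-arm difference in left-sided counts then has SD √(n/2), with n per arm. Thirteen points is 4 of 30 or 6 of 45.

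- 30 per arm (evaluable): SD 3.87; P(difference ≥ 4) ≈ 2 × [1 − Φ(3.5/3.87)] ≈ 37%.
- 45 per arm (half the enrolment target of 90): SD 4.74; P(difference ≥ 6) ≈ 2 × [1 − Φ(5.5/4.74)] ≈ 25%.

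Exact binomial calculation gives 36.6% and 24.6%.

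**3. Rough effect on the test, by hand.** Omitting a factor with hazard ratio h shifts the arm log hazard ratio by about ln(h) × imbalance. The standard error is about 2/√43 = 0.305, and the one-sided critical value is 0.842. At an imbalance of exactly 13.3 points:

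- h = 1.5: shift 0.405 × 0.133 = 0.054, or 0.18 SE. False-positive rate Φ(−0.842 ± 0.18) ≈ 25% or 15%.
- h = 2.0: shift 0.693 × 0.133 = 0.092, or 0.30 SE. False-positive rate ≈ 29% or 13%.

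**4. Simulation.** Inputs: 30 per arm, exponential times, analysis at 43 events, Cox Wald test at one-sided 0.20, 6,000 trials per row, no competing events. The strata are left out here. Each cell gives the result without and then with hemisphere in the model. The imbalance columns use a threshold of 10 points.

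| Assumed hemisphere HR | Type I, all trials | Type I, imbalance favours IMPT | Type I, imbalance against IMPT | Power, all trials |
|---|---|---|---|---|
| 1.0 | 0.193, 0.199 | 0.186, 0.193 | 0.192, 0.199 | 79.2%, 78.8% |
| 1.5 | 0.193, 0.197 | 0.236, 0.184 | 0.144, 0.201 | 78.2%, 78.9% |
| 2.0 | 0.197, 0.203 | 0.285, 0.193 | 0.112, 0.205 | 76.1%, 78.6% |

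At the 13-point threshold, for hazard ratios of 1.5 to 2.0, the model without hemisphere gives about 26-30% or 11-13% by direction, and the model with hemisphere about 17-23%. Repeat runs of the same design reached 34% and 8% at a hazard ratio of 2.0. The average power gain in the table is 0.7 and 2.5 points.

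**5. One run with competing events.** With an assumed competing hazard of 0.06 per month and hemisphere HR 2.0, overall type I error is 0.194 without hemisphere and 0.202 with it. When an imbalance of at least 10 points favours IMPT, the rates are 0.281 and 0.215. The pattern is the same.

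**The case against.** The strongest reply is that nothing is wrong with the test. Chance imbalance is already counted in the 0.20 error rate, and adjusting for the randomisation factors is a coherent, pre-specified choice. That stands. A reader might infer that omitting hemisphere inflates the one-sided 0.20 error; the type I column for all trials shows that it does not.

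A second reply is that the protocol does not assert that site or size drives cognition. That also stands: 3.2.8 poses a correlation to be studied, and 3.2.7 does the same for RPA class and MMSE. The case for hemisphere therefore rests on 12.4, where the plan itself chose to adjust these tests for side.

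A third is that failure is a decline meeting the reliable change index, and MMSE band is stratified, so baseline differences by side are partly removed. This is true of level, but not of any difference in the rate of decline. The 12.4 model keeps hemisphere even alongside baseline cognitive function.

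A fourth is that choosing hemisphere is arbitrary, since MGMT status and others could be argued for. The answer is that hemisphere already has a coding in section 12 and needs no new data. The dosimetric terms in 12.4 are different, because dose to normal brain depends on the arm.

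A fifth is that the simulation is not the planned analysis. Section 12.3 is intention-to-treat, counts non-evaluable patients as failures and uses Fine-Gray. With 45 per arm, imbalance is less frequent, and failures assigned for non-evaluability may dilute a side effect. This limits how far the figures can be carried over.

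A reader might also want tumour volume in the primary model, because section 4.0 links the amount of irradiated brain to cognition. The documents do not support requiring it. No model in section 12 contains volume. They do not say which volume would be meant, and the logarithm of residual volume is undefined after complete resection. Its effect was also not examined with competing events.

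**Conclusion.** The point holds as an avoidable gap in the primary model. The plan treats tumour side as worth adjusting for in the secondary analysis of the cognitive tests and leaves it out of the primary one, with no planned correction if the single realised allocation is uneven. The harm is conditional on that imbalance and can run in either direction; averaged over randomisations it is a power loss of about 1-2 points. The 43 events and 80% power in 12.2 are unaffected as calculated.

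The size rests on assumptions that the documents do not supply: half the tumours on each side, and a hemisphere hazard ratio of 1.5 to 2.0. If side has no effect on cognitive failure, nothing is gained and almost nothing is lost (79.2% against 78.8% power). The change is worth making because it is nearly free, and because the same adjustment made after the data are seen would be hard to defend.

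**What to change.** In 12.3, add tumour hemisphere to the pre-specified primary Fine-Gray model beside arm, RPA class, MMSE band and age group. Use the 12.4 coding, including its rule for bilateral disease. Keep the model as now written as a named sensitivity analysis. Make the change before outcome data are reviewed by arm, and record hemisphere for every randomised patient, so that the intention-to-treat analysis loses no one.

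The cost is wording and one coefficient: five instead of four on 43 events, or about 8.6 events per coefficient instead of 10.8. The MRI required by 8.4, which 13.1 has reviewed before randomisation, should supply the variable. Log tumour volume should not be required in the primary model; objective 3.2.8 can be addressed separately.
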